5.5 Definition of Baseline

For all analyses, the baseline value for each measure is defined as the last non-missing value prior to IP administration.

5.6 Multiple Records in an Analysis Window

If more than one sample is collected for CHIKV SNA NT₈₀ assessment for a given time point, the sample closest to the nominal time point is used for analysis.

5.7 Coding Dictionaries

Medical history and AEs will be coded to system organ class (SOC) and preferred term (PT) based on the Medical Dictionary for Regulatory Activities (MedDRA) dictionary version 20.1.

Prior and concomitant medications and vaccines will be coded according to the World Health Organization's (WHO) WHO-Drug Global Dictionary version B3Sep2017 to Anatomical Therapeutic Chemical (ATC) classification and preferred drug name.

5.8 Adverse Event Toxicity/Severity Grading

With the exception of redness and swelling, all solicited AEs are graded by the Investigator according to severity grading scales from "mild" to "potentially life-threatening." The

severity of redness and swelling, recorded as a diameter (mm) in the solicited adverse event memory aid, is summarized according to categories based on the largest-diameter linear measurement when a local reaction is present:

- Grade 0/absent = 0-24 mm.
- Grade 1/mild= 25-50 mm.
- Grade 2/moderate= 51-100 mm.
- Grade 3/severe= >100 mm.
- Grade 4/potentially life threatening = necrosis or exfoliative dermatitis.

Events reported as not present (0 mm is entered) are reported as Grade 0. Similarly, body temperatures recorded by the subject that are below 100.4° result in fever reported as Grade 0/absent.

Unsolicited AEs and solicited AEs other than redness and swelling are graded by the Investigator for severity. The severity grading scales (Grade 1 = Mild, Grade 2 = Moderate, Grade 3 = Severe, Grade 4 = Potentially Life-Threatening) that are used for safety assessment in this study are provided in Appendix II of this document and Section 7.1.7 and Appendix II of the Protocol, based on the *FDA Guidance for Industry: Toxicity Grading Scale for Healthy Adult and Adolescent Volunteers Enrolled in Preventative Vaccine Clinical Trials* (1). Note that AEs that result in death are classified as Grade 4 and indicated as resulting in death.

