3.3.10 Solicited Adverse Events

Solicited AEs will be collected from IP administration until Day 8. Solicited AEs for this study are local events of pain, redness, and swelling at the injection site and systemic events of oral temperature $\geq 38^{\circ}\text{C}$ (≥ 100.4 degrees Fahrenheit [$^{\circ}\text{F}$]), chills, fatigue, headache, myalgia, arthralgia, and nausea (see Section 7.1.2 and Section 7.1.2.1).

Subjects will be trained to complete a memory aid to observe, measure, and record these solicited AEs. To measure oral temperature, a digital thermometer will be provided to the subject to measure their temperature each day and record them in their memory aid. To record injection site local reactions, a ruler will be provided to the subject to measure and record the diameter of redness and swelling at the largest point of the reaction each day.

Study staff will review the signs and symptoms recorded in the memory aid. The Investigator will then assess all solicited AEs for severity (Section 7.1.7) and the action taken, and causality (Section 7.1.8). The results of the Investigator's assessment will be recorded as a separate source document and will be entered on the solicited AE CRF. Symptoms continuing beyond the solicited AE collection period will be collected and recorded on the AE CRF.

Details on definition, evaluation, reporting periods and documentation are outlined in Section 7.

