7.1.7 Severity of Adverse Events

The Investigator will grade all AEs for severity. Adverse events listed in the Grading Scale in [Appendix II](#) will be graded according to the criteria in the table. Adverse events not listed in the Grading Scale will be graded as follows:

- **Mild (Grade 1):** No interference with activity
- **Moderate (Grade 2):** Some interference with activity
- **Severe (Grade 3):** Significant; prevents daily activity

- **Potentially Life-Threatening (Grade 4):** As determined by emergency room visit or hospitalization

For the study Grading Scale see [Appendix II](#).

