8.7.2.1 Solicited Adverse Events

With the exception of redness and swelling, all solicited AEs will be summarized according to severity grading scales defined in Section 7.1.7 from “mild” to “potentially life-threatening.”

Solicited AEs will be recorded daily until 7 days post-injection (Day 8) using a memory aid. The analyses of solicited AEs will be performed by maximum severity and by treatment group. In addition, solicited AEs ongoing after 7 days post-injection (Day 8) will also be recorded as unsolicited AEs.

Frequencies and percentages of subjects experiencing each solicited AE will be presented by maximum severity. Summary tables showing the occurrence of any local or any systemic solicited AE overall and at each time point will also be presented.

The severity of redness and swelling, recorded as diameters (mm), will be summarized according to categories based on the largest diameter linear measurement when the local reaction is present:

- Grade 0/absent = 0–24 mm
- Grade 1/mild= >24–50 mm
- Grade 2/moderate= >50–100 mm

- Grade 3/severe = >100 mm
- Grade 4/potentially life threatening = necrosis or exfoliative dermatitis

Refer to [Appendix II](#).

Events reported as not present (0 mm is entered) will be reported as Grade 0.

The following summaries of solicited events will be performed:

1. Solicited events by day post-injection for each event and for any event.
2. Time of first onset of solicited AEs, for each event and any event.
3. Solicited AEs by maximum event severity, for each event and for any event.
4. Duration of solicited AEs, for each event and any event.

Solicited AEs, occurrence of at least one event by category (local, systemic), will also be included.

Only subjects with at least one observation (i.e., any non-missing values but excluding “Not done/unknown”) for the solicited AEs will be summarized.

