APPENDIX II GRADING SCALE

EVENT	MILD (Grade 1)	MODERATE (Grade 2)	SEVERE (Grade 3)	POTENTIALLY LIFE THREATENING (Grade 4)
Fever	$\geq 100.4-101.1^{\circ}\text{F}$ ($\geq 38.0-38.4^{\circ}\text{C}$)	$\geq 101.2-102^{\circ}\text{F}$ ($\geq 38.5-39^{\circ}\text{C}$)	$\geq 102.1^{\circ}\text{F}-104^{\circ}\text{F}$ ($\geq 39^{\circ}\text{C}-40^{\circ}\text{C}$)	$>104^{\circ}\text{F}$ ($>40^{\circ}\text{C}$)
Headache	No interference with activity	Some interference with activity, may require repeated use of non-narcotic pain reliever for more than 24 hours	Significant, prevents daily activity, any use of narcotic pain reliever	ER visit or hospitalization
Fatigue	No interference with activity	Some interference with activity	Significant, prevents daily activity	ER visit or hospitalization
Myalgia	No interference with activity	Some interference with activity	Significant, prevents daily activity	ER visit or hospitalization
Nausea	No interference with activity	Some interference with activity	Significant, prevents daily activity	ER visit or hospitalization
Chills	No interference with activity	Some interference with activity not requiring medical intervention	Prevents daily activity and requires medical intervention	ER visit or hospitalization
Arthralgia	No interference with activity	Some interference with activity not requiring medical intervention	Prevents daily activity and requires medical intervention	ER visit or hospitalization
Injection site pain	Does not interfere with activity	Repeated use of non-narcotic pain reliever > 24 hours or interferes with activity	Use of any narcotic pain reliever or prevents daily activity	ER visit or hospitalization
Injection site erythema/redness	25-50 mm*	>50 mm-100 mm*	>100 mm*	Necrosis or exfoliative dermatitis
Injection site induration/swelling	25-50 mm* and does not interfere with activity	>50 mm-100 mm* or interferes with activity	>100 mm* or prevents daily activity	Necrosis

*Revised by Sponsor

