APPENDIX II TOXICITY GRADING SCALE

EVENT	MILD (Grade 1)	MODERATE (Grade 2)	SEVERE (Grade 3)	POTENTIALLY LIFE THREATENING (Grade 4)
Fever	≥100.4-101.1°F (≥38.0-38.4°C)	≥101.2-102°F (≥38.5-39°C)	≥102.1°F-104°F (≥39°C-40°C)	>104°F
Headache	No interference with activity	Some interference with activity, may require repeated use of non-narcotic pain reliever for more than 24 hours	Significant, prevents daily activity, any use of narcotic pain reliever	ER visit or hospitalization
Fatigue	No interference with activity	Some interference with activity	Significant, prevents daily activity	ER visit or hospitalization
Myalgia	No interference with activity	Some interference with activity	Significant, prevents daily activity	ER visit or hospitalization
Nausea	No interference with activity	Some interference with activity	Significant, prevents daily activity	ER visit or hospitalization for hypotensive shock
Vomiting	1-2 episodes/24 hours	>2 episodes/24 hours	Requires IV hydration	ER visit or hospitalization for hypotensive shock
Diarrhea	2-3 loose stools or <400 g/24 hours	4-5 stools or 400-800 g/24 hours	6 or more watery stools or >800 g/24 hours or requires outpatient IV hydration	ER visit or hospitalization
Injection site pain	Does not interfere with activity	Repeated use of non-narcotic pain reliever > 24 hours or interferes with activity	Use of any narcotic pain reliever or prevents daily activity	ER visit or hospitalization
Injection site erythema/redness	25-50 mm	51 mm-100 mm	>100 mm	Necrosis or exfoliative dermatitis
Injection site induration/swelling	25-50 mm and does not interfere with activity	51 mm-100 mm or interferes with activity	>100 mm or prevents daily activity	Necrosis

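### Swelling Grades 0 to 3 are tabulated by diameter although the cited grading scale also grades swelling by effect on activity, and the documents disagree on whether the Investigator grades it

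*SAP*

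**What the plan says.** **Tabulation rule.** SAP 5.8 states that the severity of redness and swelling "is summarized according to categories based on the largest-diameter linear measurement when a local reaction is present". Protocol 8.7.2.1 says the same: severity "will be summarized according to categories based on the largest diameter linear measurement when the local reaction is present". In whole millimetres the bands are 0-24 (Grade 0, absent), 25-50 (Grade 1), 51-100 (Grade 2) and above 100 (Grade 3). In both places Grade 4 is necrosis or exfoliative dermatitis, for redness and swelling alike.

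**Grading scale.** Protocol 8.7.2.1 then refers the reader to Appendix II. SAP 5.8 names SAP Appendix II, together with Protocol 7.1.7 and Protocol Appendix II, as the scales used for safety assessment. Protocol 7.1.7 says that events listed in Appendix II "will be graded according to the criteria in the table". Swelling is listed. Its Grade 2 in the SAP appendix is "51 mm-100 mm or interferes with activity" and its Grade 3 is ">100 mm or prevents daily activity". The protocol appendix agrees, with Grade 3 as ">100 mm* or prevents daily activity". Grade 1 requires no interference with activity, and Grade 4 is necrosis only. The redness row uses diameter alone for Grades 1 to 3, so the mismatch at those grades is specific to swelling.

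**Who grades.** SAP 5.8: "Unsolicited AEs and solicited AEs other than redness and swelling are graded by the Investigator for severity". Protocol 3.3.10: "The Investigator will then assess all solicited AEs for severity", with the result entered on the solicited AE CRF. Protocol 7.1.7 has the Investigator grade all AEs, and SAP 9.2.2 has the Investigator assess solicited AE severity. None of these last three makes an exception for swelling.

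**The concern.** The incidence of solicited AEs through Day 8 is a secondary endpoint in the protocol. The SAP presents these events by maximum severity (Table 14.3.2.2) and in a separate table of Grade 3 or higher events (Table 14.3.2.3). A reader will take the grades in those tables as Appendix II grades. For swelling they are not: a swelling that is Grade 3 on the scale because it prevents daily activity can appear as mild or moderate and be missing from the Grade 3 table.

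The disagreement on who grades adds a second problem. If the Investigator follows Protocol 3.3.10 and 7.1.7, an Appendix II swelling grade may sit on the CRF while the table shows a different one. In addition, solicited events continuing past Day 8 are also recorded as unsolicited AEs, which SAP 5.8 has the Investigator grade. One persistent swelling could therefore carry two grades across the planned outputs.

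**Working it through.** The plan gives no figure to reproduce on this point; its sample size is stated to be practical. The check compares the two swelling rules over all combinations of diameter band and effect on activity.

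Inputs:
- Diameter grade (SAP 5.8, Protocol 8.7.2.1): 0-24 mm = 0; 25-50 mm = 1; 51-100 mm = 2; above 100 mm = 3.
- Activity grade (swelling row, both appendices): interferes = 2; prevents daily activity = 3; no effect adds nothing (0).
- Scale grade = the higher of the two. Tabulated grade = diameter grade.

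| Diameter | Tabulated | Scale: no effect | Scale: interferes | Scale: prevents |
|---|---|---|---|---|
| 0-24 mm | 0 | 0 | 2 (tabulated lower) | 3 (tabulated lower) |
| 25-50 mm | 1 | 1 | 2 (tabulated lower) | 3 (tabulated lower) |
| 51-100 mm | 2 | 2 | 2 | 3 (tabulated lower) |
| >100 mm | 3 | 3 | 3 | 3 |

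**25 mm and above.** There are 3 × 3 = 9 combinations. Three are tabulated lower: by 2 − 1 = 1 grade, 3 − 1 = 2 grades and 3 − 2 = 1 grade. None is tabulated higher. Five of the nine are Grade 3 on the scale (three above 100 mm, two at 25-100 mm), and two of those five are tabulated below Grade 3.

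**Below 25 mm.** If the *or* in the Grade 2 and Grade 3 cells applies at any size, two more combinations are lower (2 vs 0 and 3 vs 0) and are tabulated as absent. The total is then 5 of 12 lower and 0 higher, and 3 of 6 scale Grade 3 combinations drop below Grade 3.

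**Grade 4.** SAP 5.8 and Protocol 8.7.2.1 accept exfoliative dermatitis for swelling; both appendices give necrosis only. A swelling with exfoliative dermatitis and no necrosis would be tabulated as Grade 4 but be at most Grade 3 on the scale. Here the tabulated grade is the higher one.

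**Persistent swelling.** Take a 30 mm swelling that prevents daily activity and is still present after Day 8. It is Grade 1 in Table 14.3.2.2 by diameter. Graded by the Investigator on Appendix II as an unsolicited AE, it is Grade 3 in Table 14.3.5.2. Table 14.3.3.1 combines solicited and unsolicited events by highest severity, and no text says how the two grades are to be reconciled.

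**Size per subject.** With 25 subjects, one subject moved across the Grade 3 line changes the percentage by 1/25 = 4.0 points. The documents give no rate of activity-limiting swelling, so the expected number of such subjects cannot be computed.

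**The case against.** The strongest answer is that the diameter rule is deliberate. Both documents take redness and swelling out of the general severity scales and list the bands. A specific rule for a ruler measurement normally prevails over a general scale. In SAP 5.8 the reference to Appendix II follows a sentence that leaves swelling out, so it can be read as meant for the other events. How swelling is summarized and who assesses it are also separate matters: the Investigator could grade it while the table uses diameter.

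Much of this stands. There is no doubt which category the plan tabulates, and a reader who inferred that the rule is ambiguous would go too far. What remains is that no text sets the activity criteria aside for swelling. Both appendices keep a swelling row containing them, Protocol 7.1.7 applies that row, and Protocol 8.7.2.1 itself points to it. The exemption in SAP 5.8 also remains at odds with Protocol 3.3.10, Protocol 7.1.7 and SAP 9.2.2.

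Other points limit the consequence. Both documents call 0-24 mm absent, so the two lowest-band combinations depend on how the *or* is read. Of the five combinations, only those two could change incidence; the other three change severity alone. Injection site pain is itself graded by activity, so the any-event rows may already capture some of these subjects. Swelling persisting past Day 8 gets an Investigator grade as an unsolicited AE, and solicited AEs are listed by subject. The study is single-arm and tests no hypothesis.

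**Conclusion.** The point holds in a limited form. For swelling of 25 to 100 mm, the tabulated grade can be one or two grades below the Appendix II grade (three combinations). If the activity criterion applies below 25 mm, a graded swelling can also be tabulated as absent (two more). The documents conflict on whether the Investigator grades swelling, so a differing grade may be on the CRF.

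Three stronger readings are not supported:
- That the plan always understates swelling severity. At Grade 4 the difference can run the other way.
- That 5 of 12 is a rate. It counts combinations, two of which depend on the reading below 25 mm, and says nothing about how often they occur.
- That the other irregularities in the scales strengthen the point. The gaps between the protocol's arthralgia and chills grades, the absence of those rows from SAP Appendix II, the different Grade 4 nausea wording, and 39.0 °C falling in two Celsius fever bands are minor wording alignments and do not bear on swelling.

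The effect is confined to descriptive AE severity tables and arises only if activity-limiting swelling (or, at Grade 4, exfoliative dermatitis) occurs. Immunogenicity results are untouched. The textual mismatch is certain; its practical size is unknown.

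**What to change.** Before database lock, reconcile SAP 5.8, SAP 9.2.2 and SAP Appendix II with Protocol 3.3.10, 7.1.7, 8.7.2.1 and Appendix II on how swelling is graded, including the Grade 4 wording, and by whom. First check whether the solicited AE CRF captured an Investigator swelling grade. The CRF is not among the documents, and diameter is the only swelling measurement that Protocol 3.3.10 asks subjects to record.

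- **If an Investigator Appendix II grade was captured:** keep the pre-specified diameter table. Also present maximum severity and the Grade 3 or higher table using the higher of that grade and the diameter category. Record this as a change from Protocol 8.7.2.1.
- **If not:** footnote the solicited AE tables to say that swelling is graded by diameter and not on the full Appendix II scale.

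The cost is a short clarification in the SAP plus either one derivation with the added tables or a footnote. No new data are collected. Altering the protocol's scale rows would need an amendment. The downside of the first route is that some swelling grades may rise and the departure from Protocol 8.7.2.1 must be documented. The minor scale wording can be aligned in the same pass.

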6 STATISTICAL CONSIDERATIONS

6.1 Statistical Considerations

Data summaries are tabulated for selected analysis populations defined in Section 5.2.

Continuous endpoints are summarized by descriptive statistics including number of non-missing observations (n), mean, standard deviation (SD), median, minimum and maximum. In the analysis of the CHIKV-luc assay data and ELISA IgG and IgM as continuous variables, values are logarithmically transformed (base10), and the GMTs and associated 95% CI for each treatment group are computed by exponentiating the corresponding log-transformed means and two-sided 95% CIs. Categorical variables are summarized by frequency counts (n) and percentages of subjects (%) in each category, including missing or unknown when appropriate. Unless otherwise specified, CIs and hypothesis tests are two-sided with 95% confidence.

The reporting conventions to be applied to all tables, listings and figures are included in a living document that accompanies the table and listing shells. All derivations, statistical analyses, summaries and listings are generated using SAS Version 9.4 or higher (SAS Institute, Inc., Cary, North Carolina, United States).

6.1.1 Seroresponse Rates

The immune response to PXVX0317 vaccine will be demonstrated at Day 22 using seroresponse rate (the proportion of subjects with a CHIK-luc assay CHIKV SNA NT₈₀ ≥provisional threshold of 40, should a definitive seroresponse threshold not be determined prior to final analysis). Proportions of subjects with CHIKV-luc assay CHIKV SNA NT₈₀ ≥provisional threshold of 40 will be reported with associated two-sided 95% Wilson score method CIs (keyword /BINOMIAL (WILSON) on tables statement).

In addition, proportions of subjects meeting other CHIKV SNA titer thresholds ($\geq 15, 40, 60, 80, 100, 160, 640$, and 4-fold rise over baseline) will be summarized. Proportions of subjects meeting other CHIKV SNA titer thresholds will be reported with associated two-sided 95% Wilson score method CIs. See Section 8.1.7 for analysis outputs.

Identical methods will be used for analysis of seroresponse rates at Days 8, 15, and 57.

6.1.2 Geometric Mean Titers and Geometric Mean Fold Increase

The immunogenicity of PXVX0317 vaccine will be explored further using Day 22 GMTs. The mean and two-sided 95% CIs of the log₁₀-transformed CHIKV SNA titers (log₁₀) will be calculated and then back transformed and reported as the group GMT value with associated CI. Identical methods will be used for CHIKV ELISA IgG and IgM GMTs, as well analysis of GMTs at Days 8, 15, and 57. See Section 8.1.4 for analysis outputs.

Geometric mean fold increase (GMFI) from baseline (Day 1) to Days 8, 15, 22 and 57 will be calculated using the difference from Day 1 in log₁₀-transformed titers for both CHIKV SNA titers and CHIKV ELISA IgG and IgM titers with the geometric mean and 95% CI for fold increase calculated as mentioned above for GMT. The median, minimum and maximum titers and fold-increases will be based on the non-transformed scale. See Section 8.1.6 for analysis outputs.

6.2 Units and Precision

No intermediate rounding will be performed in SDTM datasets; only final values for TLFs will be rounded as follows. Immunogenicity titers will be reported with one decimal place or two significant digits (e.g., 0.032, 18.0).

Vital signs data will be reported using standard international units. Vital signs variables including derivations thereof will be reported to the same precision as the source data. Parameters derived directly from source data (e.g., minimum, maximum) or first-order statistics (e.g., mean) will be reported and analyzed with the same precision as the source data. Second-order statistics (e.g., SD) will be reported with one more significant digit than the source data. Percentages will be reported to one decimal place.

6.3 Derived Variables

This section provides definitions of the derived variables. In some cases, the definitions are provided in the relevant sections as noted.

AE, causing study discontinuation, is defined as a Yes response to the corresponding question on the AE eCRF.

AE, medically attended (MAAE), is defined as a Yes response to the corresponding question on the AE eCRF.

AE, related, is defined as one that is “probably” or “possibly” related to IP per Investigator assessment on the eCRF. If the relationship is missing for one or more occurrences of an AE for a given subject, the closest relationship of the remaining occurrences of the AE for that subject will be used; if the relationship is missing for the only occurrence of an AE for a given subject, then that event will be assumed to be related in order to be conservative.

AE, resulting in death, is defined as a Yes response to the corresponding question on the AE eCRF and/or a fatal outcome.

AE, serious, is defined per the derived eCRF field for AE seriousness, based on the individual criteria that make an AE qualify as serious (results in death, is life threatening, requires inpatient hospitalization or prolongation of existing hospitalization, results in persistent or significant disability/incapacity or is a congenital anomaly or birth defect, or any important medical event such as an event that may jeopardize the subject or require medical or surgical intervention to prevent one of the above outcomes).

AESI is defined in this study as new onset or worsening arthralgia that is medically attended, as noted by an AE coded to any of the narrow or broad preferred terms included in the MedDRA Standard Query (SMQ) for arthritis (see Appendix III) or having a Yes response to the corresponding AESI question on the AE eCRF.

AE, severity, is graded Grade 1 (mild) to Grade 4 (potentially life-threatening) as described in Section 5.8. If the severity is missing for one or more occurrences of an AE for a given subject, the maximum severity of the remaining occurrences of the AE for that subject will be used; if the severity is missing for the only occurrence of an AE for a given subject, then that event will be assumed to be severe in order to be conservative.

AEs, solicited, are defined as those collected in the memory aid. Solicited AEs include local (i.e., pain, redness, and swelling) and systemic reactions (i.e., fever, chills, fatigue, headache, myalgia, arthralgia, and nausea).

AE, treatment emergent. AE collection begins at Day 1 (baseline), the day of IP administration. AEs occurring after a subject has given informed consent, but before vaccination, will be excluded from summaries. Only treatment-emergent AEs will be summarized.

AEs, unsolicited, are defined as those AEs not listed in the memory aid but collected in the EDC.

Age at screening visit is automatically calculated by EDC based on date of birth versus date of informed consent. Age at screening will be summarized in all applicable outputs.

Analysis visits are defined in Section 5.4.

Analysis populations are defined in Section 5.2.

Baseline is defined in Section 5.5. Change from baseline is defined as (value at post-baseline assessment – value at baseline).

Baseline seropositive rate is defined as the percentage of subjects with CHIKV-luc NT₈₀ \geq lower limit of quantitation (LLOQ).

Body mass index at screening visit is automatically calculated by EDC as a subject's weight in kg divided by height in m².

Chikungunya virus ELISA IgG and IgM titers are defined per commercial test kits (InBios) utilizing a sandwich method with horseradish peroxidase plus 3,3',5,5'-tetramethylbenzidine optical density quantitation. CHIKV ELISA IgG and IgM values below the LLOQs for each will be replaced by LLOQ/2 in the immunogenicity analyses including GMT and GMFI.

Chikungunya virus luciferase neutralization assay (CHIKV-luc) SNA NT₈₀ (80% neutralizing titer) is defined as the dilution factor that corresponds to an 80% reduction of luciferase activity compared to virus-only control. CHIKV-luc assay CHIKV SNA NT₈₀ values below the LLOQ will be replaced by LLOQ/2 in the immunogenicity analyses including GMT and GMFI. For the 4-fold rise over Day 1 (baseline), values below the LLOQ will be replaced with the LLOQ.

Completion of study for an individual subject is defined as completion of the Day 183/EOS visit and any required safety follow-up (i.e., a disposition status of completed).

Early discontinuation for an individual subject is defined as completion of the Early Discontinuation Visit (i.e., a disposition status other than completed).

Medical history items entered on the medical history eCRF will be considered to predate the study regardless of onset date.

Medication, concomitant, is defined as one taken after start of IP administration on Day 1 (baseline) through the end of study. For analysis purposes, any medication which is ongoing or with a stop date that is on or after the study medication administration date will be categorized as a concomitant medication. Partial or missing concomitant medication start and/or end date will be imputed according to Section 6.5.1.

Medication, prior, is defined as one with a stop date within 30 days prior to the screening visit (90 days for blood products and within 6 months for immunosuppressive/immunomodulatory medications) through the start of IP administration on Day 1 (baseline).

Protocol deviations are defined by inclusion in the CTMS protocol deviation module (subject-level only, not site-level), including monitor-identified deviations as well as Sponsor-identified programmatic deviations. Protocol deviations will be classified by category and type (important/not important).

Rounding of values is described in Section 6.2.

Seroresponse rate is defined as the percentage of subjects who achieve a CHIKV-luciferase (luc) assay 80% neutralizing titer (NT₈₀) \geq provisional threshold of 40, should a definitive seroresponse threshold not be determined prior to final analysis.

Study Day 1 is defined as the day of IP administration on Day 1 (baseline). The day prior to Day 1 is Day -1. There is no Day 0. If the subject is not treated, then the Day 1 (baseline) is defined as the day of planned treatment.

Study day relative to Day 1 will be calculated as:

- **Study Day** = (assessment date – date of Day 1 + 1) if the assessment is on or after Day 1.
- **Study Day** = (assessment date – date of Day 1) if the assessment is before Day 1.

For conversion of durations, 1 year = 365.25 days and 1 month = $365.25/12 = 30.4375$ days.

Subgroups for sex (male and female) and race (white and non-white) are defined based on the corresponding demographic questions. Subjects missing sex or race will be omitted from analyses by subgroup.

Summary statistics are described in Section 6.1.

Time duration (in days) between event A and event B is (date of event B – date of event A + 1). For conversion of durations, 1 year = 365.25 days and 1 month = $365.25/12 = 30.4375$ days.

Treatment, actual, is defined as the treatment administered to the subject by the site (i.e., PXVX0317).

